7. STUDY POPULATION SUMMARIES

7.1 Subject Disposition

Subject disposition information will be summarized for all subjects. Summaries will include: the number of screen failures, the number of enrolled subjects, the number of subjects with successful IUS insertion (first and second attempt), the number of subjects who discontinued after failed insertion, the number of subjects in each analysis population, the number of subjects completing each visit and the study, and the primary reason for discontinuation.

7.2 Protocol Deviations

The following will be considered major protocol deviations as they could potentially affect the primary efficacy outcome:

- Did not meet all inclusion/exclusion criteria
- Used prohibited concomitant medications or therapies
- Missed treatment phase Visit 7 cycle 3 MBL analysis or Visit 8, cycle 6 MBL analysis
- Had treatment cycles collected out of window ($> \pm 2$ days from the protocol specified start date)
- Had treatment cycles collected beyond validated product stability (> 56 days)

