that counteracts the degradation of fibrin clots that form to induce hemostasis during the menstrual phase. Nonsteroidal anti-inflammatory drugs inhibit cyclooxygenase and limit the production of inflammatory mediators that can lead to increased and prolonged tissue damage during menstruation (Maybin and Critchley, 2016).

Hormonal treatments for HMB include oral or injectable progestins, combined hormonal contraceptives (CHCs) and intrauterine systems (IUSs). CHCs decrease menstrual flow and reduced symptoms for women with HMB (Bahamondes et al., 2015). During the menstrual cycle, progesterone levels sharply decline in the absence of pregnancy and trigger an influx of inflammatory mediators into the endometrial environment, leading to shedding and menstruation. However, maintenance of progesterone levels, as with progestin-only therapies or contraceptives containing estrogen and progestin, limits endometrial inflammation and prevents menstruation, resulting in an effective HMB treatment (Maybin and Critchley, 2016). CHCs are available as oral pills taken daily, vaginal rings used monthly, or patches changed weekly.

In the early 1990s, the progestin-releasing IUS containing levonorgestrel (LNG) 52 mg emerged as an option for medical management of HMB. While combined oral contraceptives, NSAIDs, and antifibrinolytics can reduce MBL by 50% within a few cycles of treatment, a LNG 52 mg IUS can decrease menstrual loss by 71% within 6 months and up to 94% after 1 year. Additionally, the LNG IUS can lead to greater improvement in women's assessment of the effect of HMB on their daily routine and psychological and physical well-being compared to usual medical treatment (Gupta et al., 2013; Qiu et al., 2014; Maybin and Critchley, 2016; Kaunitz et al., 2010). An IUS has the additional advantage of a "fit and forget" method that increases patient compliance.

A substantial body of literature has demonstrated the efficacy of the LNG 52 mg IUS in the treatment of HMB, including idiopathic HMB, HMB associated with leiomyomas and adenomyosis, and abnormal uterine bleeding. In these studies, reductions in MBL, resolution of anemia, and improvements in health-related quality of life were noted. The LNG 52 mg IUS is considered a first-line treatment for HMB (Espey, 2013). Currently only one LNG IUS, Mirena[®], is approved in the U.S. for HMB treatment in women who choose to use intrauterine contraception as their method of contraception (Mirena Package Insert). The

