5.5 Concomitant and Excluded Therapy

Concomitant medications are any prescription medications or over-the-counter preparations used by the subject beginning 30 days prior to screening through IUS discontinuation (Visit 8/Early Discontinuation) and for those subjects with continuing evaluation of an ongoing IUS-related or IUS procedure-related adverse event through resolution or stabilization. All concomitant medications, including excluded therapies, must be documented in the Concomitant Medication CRF. Subjects who use excluded therapies may require discontinuation from the study. The Medical Monitor should be contacted to discuss possible discontinuation of these subjects.

The following concomitant therapies are excluded while on study treatment:

- Hormonal contraceptives
 - *EXCEPTION: emergency contraception in any situation when the subject feels the IUS expelled, she subsequently had intercourse and was not using any other permitted method of contraception (e.g., barrier or sterilization)*
 - Subjects will not be discontinued from the study because of emergency contraceptive use if the IUS is eventually identified to be in the correct location in the uterine cavity
- Use of antifibrinolitics, platelet aggregation inhibitors, anticoagulants or other similar medications that can increase or decrease bleeding
 - *EXCEPTION: NSAIDs can be used as second-line treatment for pain management.* Acetaminophen should be the first line treatment for pain management but if not effective then NSAID use is allowed
- Iron or folate supplement use are allowed if currently in use at screening entry but initiation of any new iron or folate supplementation during study participation is allowed only for the treatment of clinically significant iron-deficiency anemia
- Any non-contraceptive estrogen, progesterone, testosterone, or gonadotropin (e.g. hCG)
- Misoprostol on the day before or day of IUS insertion or removal
- Any investigational treatment or medication other than the LNG20 IUS (experimental diagnostic testing is allowed but may not substitute for any study required evaluations)

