4. DETERMINATION OF SAMPLE SIZE

The sample size estimate of 100 subjects is based on results from previous studies with similar endpoints as well as the goal of a lower 95% confidence around the point estimate of the primary outcome with acceptable precision, i.e., being no more than 10% lower than the point estimate. The estimation of the required number of subjects needed to evaluate the efficacy of the LNG20 IUS is based on the following assumptions:

- The expected successful treatment rate is estimated to be 80% or higher
- The lower bound of 95% confidence interval should be within 10% from the point estimate, i.e., 70% or higher to establish the efficacy of LNG20 IUS for the treatment of HMB
- Early discontinuations due to dropouts, IUS expulsions, pregnancies and other reasons will not exceed 15%

A sample size of 80 - 85 subjects completing the Treatment Phase will provide at least 71.2% lower bound of the 95% confidence interval for an expected successful treatment rate of 80% or higher based on normal approximation. Therefore, 100 subjects using LNG20 IUS with an expected dropout rate of 15 - 20% will provide sufficient number of subjects, for the goal of approximately 80 - 85 subjects completing the trial.

Subjects who discontinue treatment for any reason other than a one-time study IUS replacement within two weeks of a complete or partial expulsion will not be replaced.

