5. GENERAL ANALYSIS CONSIDERATIONS

5.1 Data Summaries

Summary tables, figures, and data listings will be used to report the efficacy and safety outcomes for this study. Continuous variables will be summarized with means, standard

deviations, medians, minimums, and maximums. Categorical variables will be summarized by counts and by percentage of subjects in corresponding categories. No formal statistical testing will be performed for this study for the primary and secondary analysis.

The primary outcome measure, the proportion of subjects with successful treatment defined as end of treatment MBL <80 mL and 50% or less than baseline, will be analyzed with 95% confidence interval based on normal approximation. LNG20 IUS efficacy for the treatment of HMB will be established in this study if the lower bound of the 95% confidence interval equals or exceeds 70%.

Individual subject data obtained from the case report forms (CRFs) and any derived data will be presented by subject in data listings. Listings that include derived data fields (e.g., estimates for missing adverse event onset dates) will include the original reported data and the derived value.

All forms of output described in this plan or any amendment that follows prior to any database cut-off for analyses or final database lock are considered *a priori* considerations. Any analyses performed subsequent to database cut-off or final database lock will be considered post-hoc and exploratory. Post-hoc analyses will be identified in the CSR.

All analyses and tabulations will be performed using SAS® Version 9.3 or higher. Tables, figures, and listings will be generated in RTF/DOC (MS Word-readable) and presented in PDF format. Upon completion, all SAS programs will be validated by an independent programmer. In addition, all program output will undergo a senior level statistical review. The validation process will be used to confirm that statistically valid methods have been implemented and that all data manipulations and calculations are accurate. Checks will be made to ensure accuracy, consistency with this plan, consistency within tables, and consistency between tables and corresponding data listings. Upon completion of validation and quality review procedures, all documentation will be collected and filed by the project statistician or designee.

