9.2 Primary Efficacy Variables

The primary outcome measure will be the proportion of subjects with successful treatment of heavy menstrual bleeding based on the decrease in MBL from baseline to end of treatment after initial LNG20 IUS insertion. For the MITT and PP analysis populations, end of treatment will be defined as the last post baseline MBL value (either Treatment Cycle 3 or Treatment Cycle 6) recorded for the subject.

For the ITT-based analysis population, subjects who lack both a Treatment Cycle 3 and Treatment Cycle 6 MBL result will have the baseline MBL serve as the end of treatment recorded outcome.

A subject with successful treatment will be defined as:

- the end of treatment MBL <80 mL, and
- a decrease to a value of no greater than 50% of the baseline MBL.

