10. METHODS OF EFFICACY ANALYSIS

10.1 Primary Efficacy Outcome

The primary efficacy analysis of the proportion of subjects with successful treatment of HMB from baseline to end of treatment (based on the last post baseline MBL value up to Treatment Cycle 6) will be presented with 95% confidence interval based on normal approximation of binomial distribution.

Subjects who are lost-to-follow-up (LT FU) or withdrew consent prior to Treatment Cycle 6 evaluation are considered a subset with truly missing information. In particular, within

the context of the Covid-19 pandemic, it could be reasonably argued that they may simply have been unable or unwilling to appear for an investigational site visit. Therefore, in order to evaluate the appropriateness of procedures for handling missing data, the following approaches to data analysis will be used (as described in SAP [Sections 5.3.3 and 6](#)):

1. MITT population with LOCF: results from this approach will be considered the principal analysis finding for this study.
2. ITT population with LOCF.
3. ITT population excluding subjects LTFU or withdrew consent without study IUS removal with LOCF.

Additional assessments using the supportive MITT and PP populations will be conducted as mentioned in SAP [Section 6](#).

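### A woman whose end-of-treatment MBL passes both success criteria while she is using an excluded bleeding-reducing therapy is never counted as unsuccessful in any planned analysis

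*SAP*

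**What the plan says.** Protocol 5.5 excludes, during study treatment, hormonal contraceptives, non-contraceptive hormones, and antifibrinolytics and similar drugs that alter bleeding. There are two exceptions: second-line NSAIDs for pain, and emergency contraception after a suspected expulsion. Every use must be recorded on the Concomitant Medication CRF. The stated consequence is discretionary: "Subjects who use excluded therapies may require discontinuation from the study", with the Medical Monitor to be contacted. Protocol 7.17.1 likewise names excluded-therapy use as something for which the investigator or sponsor may stop treatment.

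SAP 7.2 counts "Used prohibited concomitant medications or therapies" as a major deviation. SAP 6 removes women with major deviations from PP only where the deviation is found to affect the MBL data.

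For MITT and PP, SAP 9.2 states that "end of treatment will be defined as the last post baseline MBL value", from Cycle 3 or Cycle 6. Success is an MBL under 80 mL that is also no more than half of baseline. Under SAP 5.3.3 a Cycle 3 value stands in for a missing or invalid Cycle 6. In the ITT analyses, baseline is carried forward only for women with neither value (SAP 6, 9.2).

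SAP 10.1 says the success proportion "will be presented with 95% confidence interval based on normal approximation of binomial distribution". Under SAP 5.1, efficacy "will be established in this study if the lower bound of the 95% confidence interval equals or exceeds 70" per cent.

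**The concern.** The trial has one arm, so the success proportion is credited wholly to the IUS. Protocol 1 says of other treatments: "While combined oral contraceptives, NSAIDs, and antifibrinolytics can reduce MBL by 50% within a few cycles of treatment". A 50% fall is exactly the second success criterion. Protocol 7.1.1 also reports that 22% of women on oral MPA, without an IUS, were successes in a randomised study that used essentially the same two-part definition. An excluded drug can therefore produce, or help to produce, a passing value.

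The SAP already applies the underlying principle elsewhere. SAP 9.1 invalidates a collection if the IUS turns out not to have been in place, because that blood loss cannot be credited to it. A value lowered by an excluded drug raises the same attribution problem but has no rule. At stake is whether a few such women could carry the result over the 70% bound without any planned analysis scoring them the other way.

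**Working it through.** **Step 1. Trace her through each analysis.** Assume a recorded excluded therapy around the cycle used, and a measured MBL that meets both criteria.

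| Analysis | Value used | Rule that could act on drug use | Her status |
|---|---|---|---|
| MITT (principal) | last post-baseline MBL | none | success |
| Supportive MITT | same | none (restricts on product validation only) | success if included |
| ITT | same; baseline only if both cycles are missing | none once a value exists | success |
| ITT excluding lost to follow-up / consent withdrawn | same | none once a value exists | success |
| PP | same | removal if judged to affect MBL | removed, or success |

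SAP 9.1 gives three grounds for an invalid collection: analysis beyond 56 days, IUS not present, and a laboratory fault. Medication is not among them. SAP 5.3.3 mentions further imputation methods, but only as optional and unspecified.

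**Step 2. Can the drug alone be enough?** With baseline B, no IUS effect and a 50% drug effect, MBL = 0.5 × B. The second criterion is met exactly. The first needs 0.5 × B < 80, so B < 160 mL. For example, B = 140 gives 70 mL, a success. At B of 160 mL or more, or with a smaller drug effect, the drug alone is not enough.

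**Step 3. Reproduce the plan's figures.** SAP 4 assumes: "The expected successful treatment rate is estimated to be 80% or higher". It then states: "A sample size of 80 - 85 subjects completing the Treatment Phase will provide at least 71.2% lower bound of the 95% confidence interval". The lower limit is p − 1.96 × √(p(1 − p)/n).
- n = 80, p = 0.80: 0.80 − 1.96 × √(0.16/80) = 71.2%
- n = 85, p = 0.80: 0.80 − 1.96 × √(0.16/85) = 71.5% (the figure in Protocol 9.1)

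Both reproduce.

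**Step 4. Score k such women as unsuccessful (denominator kept), or drop them as PP would.** The documents give no k; it is an assumption shown as a range.

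| Observed | k | Scored unsuccessful | Lower limit | Dropped | Lower limit |
|---|---|---|---|---|---|
| 64/80 | 0 | 64/80 | 71.2% | 64/80 | 71.2% |
| 64/80 | 1 | 63/80 | 69.8% | 63/79 | 70.9% |
| 68/85 | 0 | 68/85 | 71.5% | 68/85 | 71.5% |
| 68/85 | 1 | 67/85 | 70.1% | 67/84 | 71.2% |
| 68/85 | 2 | 66/85 | 68.8% | 66/83 | 70.8% |
| 72/85 | 0 | 72/85 | 77.1% | 72/85 | 77.1% |
| 72/85 | 5 | 67/85 | 70.1% | 67/80 | 75.7% |
| 72/85 | 6 | 66/85 | 68.8% | 66/79 | 75.4% |

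For 66/85: p = 0.7765, and 0.7765 − 1.96 × √(0.7765 × 0.2235/85) = 0.688.

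The 70% rule is missed at k = 1 of 80 and k = 2 of 85 when observed success is 80%, and at k = 6 of 85 when it is 72/85 (84.7%). Dropping the same women leaves the rule met in every row, so PP does not stand in for scoring them as unsuccessful.

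**The case against.** The other side has several fair points.

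- **She is not automatically a success.** A reader might infer that every user of an excluded drug is counted for the IUS. The documents do not support that. She is scored on her measured MBL, and if it misses either criterion she is already a failure in MITT and ITT. Of the MPA users in Protocol 7.1.1, 78% (100 − 22) were not successes.
- **Conduct rules narrow the route.** A woman stopped before any Cycle 3 or Cycle 6 collection is outside MITT and fails in ITT through baseline carried forward. One stopped between cycles is scored on Cycle 3, which may predate the drug. Discontinuation is discretionary, however, so the route stays open.
- **The literature figure is qualified.** The 50% reduction is stated for treatment over a few cycles, not for any brief use, and Step 2 also assumes no IUS effect, whereas Protocol 7.1.1 cites about 85% success with a 52 mg LNG IUS.
- **The data are not wholly silent.** Removing apparent successes lowers the PP estimate a little, and SAP 8.1 tabulates concomitant medications by class and generic name. Neither ties use to the cycle that supplied the endpoint.
- **Use does not prove non-response.** A hormone may be taken for another reason. As-measured scoring with PP in support is a recognised choice, and which result is primary is partly a matter of estimand.

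These points limit the claim to women whose MBL passes, and they make its size uncertain. None supplies an analysis that counts such a woman as unsuccessful.

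**Conclusion.** The gap is real but conditional. It applies to women who used an excluded bleeding-reducing therapy around the cycle that supplied their end-of-treatment value and whose MBL then met both criteria. They are successes in MITT, Supportive MITT and both ITT analyses. At most they leave PP, and that depends on a judgement of impact, so it would be wrong to say that PP always removes them.

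It would also be too strong to say that one or two women generally overturn the trial. That holds only at almost exactly 80% observed success, while the plan anticipates 80% or more. The count rises to 6 of 85 at 72/85. The number of such women is unknown and may be zero. What stands is that the plan names this deviation as a threat to the primary outcome and includes no analysis that scores it against the IUS.

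**What to change.** Add to SAP 9.2 and 10.1, before database lock, an analysis of the primary outcome in MITT and ITT with this scoring rule:

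- **Who is scored as not successful.** Any woman whose Concomitant Medication CRF shows an antifibrinolytic or an excluded hormonal therapy (Protocol 5.5) during the cycle that supplies her end-of-treatment value, or within a drug-specific look-back before it. That cycle is Cycle 6, or Cycle 3 if carried forward.
- **Look-back.** Take it from the protocol's own entry exclusions: 30 days for the drugs in criteria 16, 17 and 19, and the DMPA period in criterion 18 (9 months, reducible to 6). A uniform 30 days would miss an earlier DMPA injection. Six cycles last 6 × 28 = 168 days, or 168/30.4 = 5.5 months, so any DMPA injection given on study before the measured cycle falls inside even the shorter period. For the 30-day drugs, use confined to Cycle 3 does not affect a woman with a valid Cycle 6, because 56 days (Days 85 to 140) separate the two.
- **What does not count.** Permitted second-line NSAIDs and the emergency-contraception exception.
- **Reporting.** Give the number of women affected and show this result beside the as-measured result. If only one is primary, the other is the sensitivity analysis.

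This changes scoring only, not who may receive which therapy or who is discontinued. It costs one SAP paragraph, one flag derived from an existing CRF and one extra row of results. The success rate may come out slightly less favourable, and some women scored as unsuccessful will have used the drug for reasons unrelated to IUS response. If it is left until after lock, SAP 5.1 makes any such analysis post hoc.

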7.3 Demographic and Baseline Characteristics

Demographic variables include: age, ethnicity, and race. Other baseline characteristics include: marital status, partner status, height, weight, BMI, medical history, gynecological history, menstrual history, pregnancy history, and baseline MBL.

Demographic and baseline characteristics will be summarized for the Safety and MITT populations. If the Supportive MITT and/or the PP population size are noticeably different from the MITT, the demographic and baseline characteristics will be summarized for the Supportive MITT and/or the PP population as well.

8. TREATMENT AND MEDICATION

8.1 Pre-trial and Concomitant Medications

Verbatim terms on eCRFs will be mapped to the narrowest Anatomical/Therapeutic/Chemical (ATC) class possible and generic drug names using the World Health Organization (WHO) Drug Dictionary Enhanced (DDE). For example, if the 4th level is not available, then the 3rd level (pharmacological subgroup) will be provided.

Concomitant medications include any medication or health product (any prescription medications or over-the-counter preparations) taken during the active study treatment period. Pre-trial medications include any medications taken within seven days (30 days for anticoagulants) of enrollment. Concomitant medications will be summarized by WHO ATC class and generic drug name. These summaries will present the number and percentage of subjects using each medication. Subjects may have more than one medication per ATC class and Generic Drug Name. At each level of subject summarization, a subject is counted once if she reported one or more medications at that level. Each summary will be ordered by descending order of incidence of ATC class and generic drug name within each ATC class.

8.2 Extent of Exposure

Exposure to study IUS will be summarized by treatment duration.

9. EFFICACY ANALYSES

The primary efficacy analysis will be based on the MITT population. Additional supportive efficacy analyses will be performed using the ITT (including and excluding subjects who are LTFU or withdrew consent without study IUS removal), Supportive

MITT, and PP populations, unless it is determined that the populations are essentially equivalent.

9.1 Menstrual Blood Loss

This study will utilize the AH method to assess MBL. During the Screening Phase all feminine hygiene products used during a menses with any evident bleeding will be analyzed. Baseline MBL will be the average of the Screening cycles evaluated. Two of three cycles must have ≥ 80 mL MBL to qualify for enrollment (Treatment Phase); if the first two cycles qualify a third cycle will not be evaluated. During the Treatment Phase, all feminine hygiene products use only during Cycle 3 (Days 57-84) and Cycle 6 (Days 141-168) will be collected for analysis and used to determine efficacy. All values of MBL reported by the lab for the above cycles for both validated and unvalidated feminine hygiene products will be included in the analysis, unless analyzed beyond the 56 days of validated stability.

MBL assessment measured from all collected feminine hygiene products will be included in the primary analysis and only study-specific validated feminine hygiene products in the supportive analyses.

The study-specific feminine hygiene products are:

- Tampax Regular Tampons with flushable applicator
- Tampax Super or Super Plus tampons with flushable applicator
- Kotex Regular Maxi Pads;
- Kotex Super Long Maxi Pads;
- Kotex Overnight Maxi Pads with Wings.
- Carefree Body Shape Pantiliners with Actifresh, Extra Long

A MBL assessment by AH may not be collected for Treatment Phase Cycle 3 and Cycle 6 in which a subject reported being amenorrheic (no spotting or bleeding) on the CRF for AH Menstrual Blood Loss Assessment; in this case the corresponding MBL value will be set to 0 mL. In the case that no feminine hygiene products were used by the participant due to spotting only the MBL value will be set to 0 mL.

Any feminine hygiene product collection would be considered “invalid” for the following:

- Analyzed beyond the 56 days of validated stability (from start of feminine hygiene collection).
- Any feminine hygiene product collection for a Treatment Phase cycle for which it was discovered during the post-collection interval study visit (i.e., Visit 7 for Cycle 3 and Visit 8 for Cycle 6) that the study IUS was not present
- Technical issue at the lab in analyzing the product leading to unreportable results

